1 INTRODUCTION AND RATIONAL OF THE STUDY

The development of human cancer is a multistep process characterized by the accumulation of genetic and epigenetic alterations that drive or reflect tumour progression. These changes distinguish cancer cells from their normal counterparts, allowing tumours to be recognized as foreign by the immune system. However, tumours are rarely rejected spontaneously, reflecting their ability to maintain an immunosuppressive microenvironment. Programmed death-ligand 1 (PD-L1; also called B7-H1 or CD274), which is expressed on many cancer and immune cells, plays an important part in blocking the 'cancer immunity cycle' by binding programmed death-1 (PD-1) and B7.1 (CD80), both of which are negative regulators of T-lymphocyte activation. Binding of PD-L1 to its receptors suppresses T-cell migration, proliferation and secretion of cytotoxic mediators, and restricts tumour cell killing. The PD-L1–PD-1 axis protects the host from overactive T-effector cells not only in cancer but also during microbial infections. Blocking PD-L1 therefore enhances anticancer immunity [Chen].

Atezolizumab treatment

Atezolizumab is a human monoclonal antibody based on a human IgG1 framework containing heavy chain V_HIII and light chain V_KI subgroup sequences. The recombinant antibody consists of two heavy chains (448 amino acid residues each) and two light chains (214 amino acid residues each) with inter- and intra-chain disulfide bonds that are typical of IgG1 antibodies. Atezolizumab incorporates an amino acid substitution (asparagine to alanine) at position 298 in the CH2 domain of each heavy chain resulting in a non-glycosylated antibody that has minimal binding to Fcγ receptors and, consequently, prevents Fc-effector function and depletion of cells expressing PD-L1 at expected concentrations in humans. Therefore, atezolizumab lacks the N-linked oligosaccharides typically observed on other CHO-derived monoclonal antibodies.

Clinical Pharmacokinetics

On the basis of available preliminary PK data (0.03-20 mg/kg), atezolizumab appeared to show linear pharmacokinetics at doses ≥ 1 mg/kg. For the 1-mg/kg and 20-mg/kg dose groups, the mean apparent clearance (CL) and the mean volume of distribution at steady state (Vss) had a range of 3.20 to 4.44 mL/day/kg and 48.1 to 65.7 mL/kg, respectively, which is consistent with the expected PK profile of an IgG1 antibody in humans.

Clinical efficacy and safety

The high-affinity human monoclonal immunoglobulin-G1 (IgG1) antibody atezolizumab that specifically binds to PD-L1 and prevents its interaction with PD-1 and B7.1 was recently assessed in a dose-escalating phase I trial [Herbst]. A total of 277 patients with advanced incurable cancer received atezolizumab intravenously every 3 weeks. Mean single-dose atezolizumab pharmacokinetics were consistent with a typical IgG1 at doses ≥1 mg kg−1, with a mean terminal serum half-life of ~3 weeks. Overall, treatment was well tolerated up to the maximum administered dose of 20 mg kg−1 q3w. Most adverse events (AEs) did not require medical treatment. The most common treatment-related AE was fatigue, which often occurred with low-grade fever during the first treatment cycle. Pyrexia was reported in ~21% of patients; it most commonly occurred during cycle 1 and was uncommon during subsequent cycles. Treatment-related grade 3–4 AEs were observed in 35 patients (13%) and immune-related grade 3-4 AEs were observed in 3 patients (1%). According per Response Evaluation Criteria in Solid Tumours, version 1.1 (RECIST v1.1) on 175 evaluable patients; confirmed responses (complete and partial responses) were observed in 32 of 175 (18%), 11 of 53 (21%), 11 of 43 (26%), 7 of 56 (13%) and 3 of 23 (13%) of patients with all tumour types, non-small cell lung

cancer (NSCLC), melanoma, renal cell carcinoma and other tumours (including colorectal cancer, gastric cancer, and head and neck squamous cell carcinoma), respectively. Responses could also be rapid and durable. Also, the association of tumour PD-L1 expression correlated with clinical response to atezolizumab.

Further information on this study (named study PCD4989g in the IB) and from other studies conducted with atezolizumab in monotherapy or in combination are presented in the investigator brochure.

Therapy of sarcomas represents an area of significant unmet need in oncology. Sarcoma arises from cells of mesenchymal origin with many different subtypes. Immunotherapy response is dependent on complex interactions between tumor and immune cells within the tumor microenvironment. Several factors determine whether or not the immunotherapy response will be promoted or inhibited. These include the inherent antigenicity of the tumor. Mutations in proteins and/or aberrant proteins expressed by tumor cells and the "neoantigens" they generate are the primary targets for T-cell-mediated destruction. Tumor mutation burden has emerged as a quantitative marker which can help to predict responses to immune checkpoint inhibition. The immunotherapy response is also dependent on the infiltration of immune effector cells into the tumor. Specific patterns of tumor infiltrating lymphocytes (TILs) within the tumor microenvironment are associated with improved outcome in patients with many types of cancers, regardless of the type of therapy administered.

A naturally-occurring immune infiltrate has been reported for several sarcoma subtypes. Orui et al., provided a detailed characterization of the immune infiltrates in a variety of histologic subtypes with detection of cytotoxic CD8 T cells expressing granzyme B, indicative of their cytotoxic function, the presence of dendritic cells found to be CD1a negative but CD83 positive, indicative of a mature phenotype [Orui]. Tseng et al. reported evidence suggesting an adaptive immune response with the presence of intratumoral lymphoid structures [Tseng]. In liposarcoma, CD8 T cells appear to be scattered throughout the tumor, whereas CD4 T cells and CD20 B cells were localized to these lymphoid structures. The presence of such immune infiltrate suggests that immunotherapy may potentially be effective in this subtype.

The currently available human data to support the efficacy of immunotherapy in sarcomas remain limited. An intratumoral infiltration of PD-1 positive lymphocytes was observed in 65% of cases and PDL1 tumor expression in 58% across several soft tissue sarcoma subtypes (N=105, with leiomyosarcoma (n = 20), synovial sarcoma (n = 16), undifferentiated sarcoma (n = 11), and myxoid liposarcoma (n = 10) [Kim]. The phase II study SARC028 demonstrated a RR of 40 % and 20% for undifferentiated pleomorphic sarcoma and dedifferentiated liposarcoma, respectively; under pembrolizumab treatment. Two (5%) of 40 patients with bone sarcoma had an objective response, including one (5%) of 22 patients with osteosarcoma and one (20%) of five patients with chondrosarcoma. In the STS cohort, 20 % ORR was reported by RECIST 1.1 with additional 40 % of patients with best response of stable disease. Fourmonth progression-free rate was 44 % (C.I 22-66 %) which was considered as statistically significant improvement relative to historical PFR of 20 %. [Tawbi, Burgess]. Moreover, durable responses have been seen with atezolizumab phase 2 study in advanced alveolar soft part sarcoma. The objective response rate (ORR) was 42 % with confirmed PRs in 8 out of 19 patients [O'Sullivan].

Despite the small sample size and the clinical heterogeneity of sarcoma cohort analyzed, Sharma et al., [Sharma] reported that RT induced remarkable changes in various immune cells, immune-related transcripts and cancer-testis antigens, including: a higher infiltration of both CD4+ and CD8+ T cells after radiotherapy; an upregulated expression of MHC-I and of different CT-antigens, which makes tumors more visible to CD8+ T cells; a *de novo* expression of the highly immunogenic CT-antigens in some patients; a higher expression of immune effector molecules, including perforin, granzyme B, NKG2D, IFN- γ , TNF- α , and IL-12. Of note,

recently, a complete clinical response was observed in patients with clear cell sarcoma treated with an anti-PD1 checkpoint inhibitor combined with standard fractionation radiotherapy [Marcrom].

Also, the mechanism of action of atezolizumab is associated with inflammation and/or immune-mediated adverse events including potential dermatologic, hepatic, endocrine, gastrointestinal and respiratory events. Such events should be closely monitored. Management guidelines are provided in this protocol (section 5.3.2).

Rational of the study

Although it is usually described as an immunosuppressive modality and not thought of as immunotherapy, there are new preclinical evidences suggesting that high-dose ionizing irradiation (IR) results in direct tumour cell death and augments tumour-specific immunity, which enhances tumour control both locally and distantly. Importantly, IR effects exceed the classical cytocidal properties by also causing phenotypic changes in the fraction of surviving cells, markedly enhancing their susceptibility to T cell-mediated elimination [Formenti]. However, not all IR-induced modifications of the tumour and its microenvironment favor immune rejection. The tumour microenvironment is populated by various types of inhibitory immune cells including Tregs, alternatively activated macrophages, and myeloid-derived suppression cells (MDSCs), which suppress T cell activation and promote tumour outgrowth. Chiang et al. showed the accumulation of pro-tumourigenic M2 macrophages in areas of hypoxia present in irradiated tumours [Chiang]. IR then may also induced responses that are inadequate to maintain antitumuor immunity.

Close interaction between IR, T cells, and the PD-L1/PD-1 axis exsit and provide a basis for the rational design of combination therapy with immune modulators and radiotherapy. Deng et al. demonstrate that PD-L1 was upregulated in the tumour microenvironment after IR. Moreover, administration of anti-PD-L1 enhanced the efficacy of IR through a cytotoxic T cell-dependent mechanism. Concomitant with IR-mediated tumour regression, IR and anti-PD-L1 synergistically reduced the local accumulation of tumour-infiltrating MDSCs, which suppress T cells and alter the tumour immune microenvironment. Finally, activation of cytotoxic T cells with combination therapy mediated the reduction of MDSCs in tumours through the cytotoxic actions of TNF [Sagiv-Barfi]. Sagiv-Barfi et al, also demonstrated in 5 patients receiving atezolizumab and radiation therapy, at least stabilization of systemic progression in all patients and a RECIST partial response at systemic sites in 1 patient. Transient, grade 1-2 inflammatory adverse events (fevers, flu-like symptoms) occurred with no serious immune-related toxicities [Sagiv-Barfi]. Abscopal out-field effects of irradiation has also been described in addition to a reduction in circulating MDSCs in a melanoma patient treated with the anti CTLA-4 ipilimumab and radiotherapy [Postow].

Lastly, recent evidence demonstrates that loco-regional curative treatment with stereotactic ablative radiotherapy (SABR) is a good alternative as compared with conventional 3D RT for patients with solid tumour, with durable remissions and a low toxicity profile. Many non-randomised studies have shown that SBRT for oligometastases is safe and effective, with local control rates of about 80%. Importantly, these studies also suggest that the natural history of the disease is changing, with 2–5 year progression-free survival of about 20% [Tree]. For colorectal, non-small cell, and renal cell cancers, 1-year metastasis control rates ranged from 67 to 91% [Salama]. Moreover, abscopal reponses in the setting of immune checkpoints inhibitors and radiotherapy combinations have been made in the setting of metastatic disease event in patients with extensive tumor burden [Postow], [Golden], [Reynders]. The goal of SABR is to deliver appropriate metastasis directed radiotherapy while minimizing exposure of surrounding normal tissues. Interestingly, the dose and fractionation employed modulate RT

ability to synergize with immunotherapy. Vanpouille-Box et al, showed that immune response genes were differentially expressed in irradiated tumours by 8Gyx3 but not 20Gyx1. This highlight the interest of hypofractionated SABR acting as a "in situ tumour vaccine" [Vanpouille-Box].

As hypofractionated SABR may, in addition to its good local control, increase the effectiveness of anti PD-L1, we aimed to investigate the efficacy and the tolerability of the combination of anti-PD-L1 antibody with SABR. Preliminary clinical data about the combination of Atezolizumab and radiotherapy in metastatic patients suggest that irradiation of one tumor site may induce disease stabilization which may last several Atezolizumab administration cycles (ie 3-6 months). These early data might reflect the fact that the systemic anti tumor response is transient. Thus, we plan to test whether focal re irradiation of a previously un irradiated tumor site might re induce systemic anti tumor response in the case of disease re evolution for patients progressing after initial stabilization of their disease. These data are in line with one of the first prospective clinical trial aimed at evaluating abscopal effect which performed radiation therapy to 2 distinct tumor sites separated from several weeks [Golden].

Shaverdian et al. showed that radiotherapy, given before PD-1/PD-L1 inhibition, could increase PFS and OS over PD-1/PD-L1 inhibition alone [Shaverdian]. This study included 98 patients from the Keynote-001 trial that tested PD-1 inhibition (pembrolizumab) in progressive stage III or stage IV NSCLC. Very interestingly, median PFS was increased by 2.3 months and median OS by 6.3 months. This survival advantage was confirmed in multivariate analysis. The tumoral expression increase of PD-L1 in these studies may partly have increased the tumour sensitivity to PD-1/PD-L1 inhibition.

2 STUDY OBJECTIVES

2.1 Primary objective

To determine the 1 year progression-free survival rate (based on RECIST v1.1.) under combined SABR and anti-PDL1 atezolizumab therapy:

- in patients with metastatic colorectal cancer (cohort closed to inclusions);
- in patients with metastatic non-small lung cancer (cohort closed to inclusions);
- in patients with metastatic renal cell carcinoma (cohort closed to inclusions);
- in patients with metastatic sarcoma (cohort closed to inclusions).

Each cohort will be analysed separately.

2.2 Secondary objectives

To determine, the progression-free survival (PFS) measured from the date of treatment initiation to the date of death or progression, whichever comes first under combined SABR and anti-PDL1 atezolizumab therapy using RECIST v 1.1 and modified RECIST (mRECIST).

To further describe, the efficacy of combination (SABR and atezolizumab) both on the irradiated lesions and the non-irradiated lesions based on tumour response indicators and clinical endpoints using RECIST 1.1 criteria and modified RECIST (mRECIST).

To determine the Treatment failure rate defined as the proportion of patients who cannot receive the planned irradiation dose or relative atezolizumab dose intensity below 75% of the initially targeted dose (i.e below 900 mg).

To evaluate the toxicity of atezolizumab in combination with SABR according to the NCI-CTCAE scale (version 4.03).

To assess tumor reponse indicators and clinical endpoints, assessed according to RECIST v1.1 at 6 weeks after the second SABR course.

In lung and sarcoma patiens who received a second SABR course after oligoprogression:

- To assess the objective response rate at 6 weeks after the second SABR course, using RECIST v1.1 and continuation of atezolizumab at the time of progression.
- To compare the modification of the size of the lesion which received the second SABR course versus the non-treated lesion (abscopal effect). Modification is assessed as the variation between the size at the time of the second SABR course and the size 6 weeks thereafter.
- To assess progression-free survival 2 (PFS2) measured from the date of the second SABR course to date of second progression or death whichever comes first. Patients alive and free of progression at the cut-off date will be censored at the last assessment date.
- Time to progression ratio (TTPr) in patient receiving a second SABR course:

To define the TTP ratio, let's denote:

- TTP1 the time from treatment initiation to the time of progression after first irradiation.
- TTP2 the time from first progression to the time of progression after the second SABR course. Patients receiving a second SABR course who die without a documented second progression will be counted as progressive as it is unlikely that patients die of a cause unrelated to the failure of the treatment and subsequent tumor progression. Patients alive and free of progression at the cutoff date will be censored at the last assessment date. Radiological progression is measured using RECIST v1.1 on the same tumor lesions over all the trial, whenever possible. TTP2 is defined as PFS2 as it is unlikely that patients die of cause unrelated to the treatment failure and subsequent tumor progression.

Exploratory objectives:

To evaluate the functional imaging changes using FDG PET/CT and tumour growth rates.

To evaluate the systemic immunologic anti-tumour response based on the sequential tumour biopsies and immunomonitoring on peripheral blood samples.

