3.1 Treatment period

Drug: The anti-PD-L1 antibody atezolizumab will be administered at a dose of 1200 mg every 3 weeks.

Atezolizumab treatment will be administered as long as:

- Patients are experiencing clinical benefit, as assessed by an investigator, and
- In the absence of unacceptable toxicity or symptomatic deterioration attributed to disease progression after an integrated assessment of radiographic data, biopsy results (if available) and clinical status.

In case of progressive disease according to RECIST v1.1 criteria, patients will be permitted to continue atezolizumab treatment if they meet all of the following criteria:

- Evidence of clinical benefit as assessed by the Investigator,
- Absence of symptoms and signs (including worsening of laboratory values, e.g., new or worsening hypercalcemia) indicating unequivocal progression of disease,
- No decline in ECOG performance status that can be attributed to disease progression, and

- Absence of tumour progression at critical anatomical sites (e.g., leptomeningeal disease) that cannot be managed by protocol-allowed medical interventions.

Patients treated with atezolizumab in whom radiographic disease progression is confirmed at a subsequent tumour assessment may be considered for continuing study treatment at the discretion of the Investigator if they continue to meet the above criteria.

SABR: Stereotactic ablative Radiation therapy will be delivered concurrently with the 2rd cycle of atezolizumab (at week 4) using 6MV photons or other energies with standard field encompassing tumour.

At least one tumour site will receive radiation and another tumour site(s) should be not treated but evaluable by RECIST v1.1 in order to proper assess potential abscopal effect.

Hypofractionated SABR will be delivered with an equivalent biologic dose (BED) > 80 Gy. The recommended fractionation is 45 Gy (3 fractions of 15 Gy) but shall be adapted upon normal tissue tolerance constraint. Total duration of radiotherapy must not exceed eight days. Tumour size will be ≤ 4 cm according to recent imaging (CT or PET). The radiation dose will be prescribed to the 90% isodose line in order to deliver 95% of the planned dose to 95% of the planned tumour volume (PTV). The dose used to treat a given metastasis will be based on the location of the metastasis, as normal tissue toxicity is likely to arise from the organs at risk surrounding the metastasis.

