7.2 Secondary criteria

7.2.1 Efficacy

- Progression-free survival (PFS) measured from the date of treatment initiation to the date of progression or death, whichever comes first. Patients alive and free of progression at the cut-off date will be censored at the last assessment date.
- Modification of the size of the irradiated and non irradiated lesion(s) as measured by its longest diameter according to RECIST 1.1 will be compared.

Assessment of efficacy endpoint listed below will be performed according to RECIST v 1.1 criteria (refer to Appendix 4: RECIST 1.1 CRITERIA) and modified RECIST (mRECIST) (refer to Appendix 5: mRECIST CRITERIA MODIFIED RESPONSE EVALUATION CRITERIA IN SOLID TUMORS).

Efficacy endpoints are:

- Disease Control Rate (DCR): complete responses (CR) + partial responses (PR) + stable disease (SD).
- Objective Response Rate (ORR): CR + PR
- Duration of response (DOR)
- Time to progression (TTP) of non irradiated lesions is computed as the delay from enrollment to the first occurrence of progression outside of the irradiated field
- Time to progression (TTP) of irradiated lesions is computed as the delay from enrollment to the first occurrence of progression of irradiated lesions;
- Evaluation of the local control, distant control.

In lung cancer and sarcoma patients receiving a second SABR course:

For patients in lung and sarcoma cohorts who can receive a second SABR course if oligoprogression, the objective response rate at 6 weeks is defined as any partial or complete response according to RECIST v1.1 observed at the first radiological evaluation (6 weeks after the second SABR course) over the number of patients that received a second SABR course.

- Size of the irradiated and non irradiated lesion(s) is measured in its longest diameter according to RECIST 1.1. Modification observed between the time of progression 1 and the value at 6 weeks will be compared between irradiated and non irradiated lesions.

- Progression-free survival 2 (PFS2) measured from the date of the second SABR course to the date of second progression or death. Patients alive and free of progression at the cutoff date will be censored at the last assessment date.
- Time to progression ratio (TTPr) in patient that received a second SABR course. To define the TTP ratio, let's denote:
 - o TTP1 the time from treatment initiation to the time of progression after first irradiation

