CT and MRI are the best currently available and reproducible methods to measure target lesions selected for response assessment. Conventional CT and MRI should be performed with cuts of 5 mm or less in slice thickness contiguously. Spiral CT should be performed using a 5 mm contiguous reconstruction algorithm. This applies to the chest, abdomen and pelvis.

Ultrasound, endoscopy and laparoscopy should not be used to measure tumour lesions or evaluate tumour response. However, these techniques can be useful to supplement information from other techniques.

Tumour markers alone cannot be used to assess response. If markers are initially above the upper normal limit, they must normalise for a patient to be considered in complete clinical response.

Cytology and histology can be used to differentiate between PR and CR in rare cases (for example, residual lesions in tumour types such as germ cell tumours, where known residual benign tumours can remain).

Baseline Documentation of Target and Non-target Lesions

All measurable lesions up to a maximum of two lesions per organ and five lesions in total, representative of all involved organs should be identified as target lesions and will be recorded, measured and numbered at baseline. The longest diameter will be recorded, except for lymph nodes, which will be measured by their short axis. Target lesions should be selected on the basis of their size (lesions with the longest diameter) and their suitability for accurate repetitive measurements (either by imaging techniques or clinically).

The sum of diameters for all target lesions will be calculated and reported as the baseline sum of diameters. The baseline sum of diameter will be used as reference to further characterize the objective tumour response of the measurable dimension of the disease (Table 1.1).

Table 1.1: Evaluation of target lesions

Complete Response (CR)	Disappearance of all target lesions. Any pathological lymph nodes (whether target or non-target) must have a reduction in short axis to <10mm)
Partial Response (PR)	At least a 30% decrease in the sum of diameters of target lesions, taking as reference the baseline sum diameters

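### The second-course abscopal effect is defined as irradiated versus untreated lesion change, a contrast that shrinks as the untreated lesion responds and so cannot measure it

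*Protocol*

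**What the plan says.** Among the objectives for lung and sarcoma patients given a second SABR course after oligoprogression, protocol section 2.2 lists: "To compare the modification of the size of the lesion which received the second SABR course versus the non-treated lesion (abscopal effect"). The synopsis states the same objective with the same label. Section 2.2 then fixes the change score: "Modification is assessed as the variation between the size at the time of the second SABR course and the size 6 weeks thereafter". Section 7.2.1 repeats the comparison with a differently worded starting point: "Modification observed between the time of progression 1 and the value at 6 weeks will be compared between irradiated and non irradiated lesions".

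The question behind the second course is given in section 1, which asks whether "focal re irradiation of a previously un irradiated tumor site might re induce systemic anti tumor response". Section 3.1 explains why a lesion is spared at the initial course: "another tumour site(s) should be not treated but evaluable by RECIST v1.1 in order to proper assess potential abscopal effect". The second course may be given under the same conditions.

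Section 7.2.1 also has a general comparison for the whole trial, without the abscopal label: "Modification of the size of the irradiated and non irradiated lesion(s) as measured by its longest diameter according to RECIST 1.1 will be compared". Appendix 4 gives the measuring rule: "The longest diameter will be recorded, except for lymph nodes, which will be measured by their short axis". Tumour growth rate appears only as an exploratory objective: "To evaluate the functional imaging changes using FDG PET/CT and tumour growth rates".

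**The concern.** The scientific question is about what happens outside the field after one lesion is re-irradiated. The measure named for it is a comparison between the lesion inside the field and the one outside. Such a comparison responds first to local ablation. For a given local effect it moves towards zero as the out-of-field response improves, which is the wrong direction for something called an abscopal effect.

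At stake is how the second-course results are read. A large difference between the two lesions could be reported under the abscopal heading when SABR has worked only on its target. Equal shrinkage of both lesions, the most favourable systemic result, could be reported under that heading as no difference. The protocol itself fixes the contrast, the label and the 6-week window, so a statistical analysis plan that followed it would inherit the problem.

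**Working it through.** **The plan's own figure.** The protocol gives no sample size, effect size or test for this contrast. Its only sizing for second-course patients (section 8.1) concerns the 6-week response rate: 10% versus 30%, one-sided alpha 10%, power 90%, success at 5 or more responses, 25 to 30 patients per cohort. With 25 patients and a threshold of 5, the exact binomial alpha is 0.098 and the power 0.910, so that design reproduces. It says nothing about the lesion contrast.

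**The identity.** Let I be the mean percentage size change of irradiated lesions and N that of untreated lesions. Read as a difference, the planned comparison is D = I − N. The abscopal question concerns N. With I fixed at −30%:

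- N = +15% gives D = −30 − 15 = −45
- N = −10% gives D = −30 + 10 = −20
- N = −30% gives D = −30 + 30 = 0

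Each further point of shrinkage in the untreated lesion takes one point off the contrast until the two lesions are equal. This needs no assumption about variability.

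**What 25 to 30 patients would show.** The standard deviation and the within-patient correlation are not in the protocol. Assumed here: SD 20 to 30 percentage points, correlation ρ from 0 to 0.6, normal approximation.

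- SE(D) = SD × √(2(1 − ρ)/n): from 20 × √(0.8/30) = 3.27 to 30 × √(2/25) = 8.49
- SE(N) = SD/√n: from 20/√30 = 3.65 to 30/√25 = 6.00

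The last two columns are illustrative tests, two-sided 5% for D and one-sided 2.5% for N. The protocol specifies neither.

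| Scenario (assumed) | I | N | D | Chance of rejecting D = 0 | Chance of showing N < 0 |
|---|---|---|---|---|---|
| Nothing works, equal growth | +15 | +15 | 0 | 5% | about 0% |
| Both stable | 0 | 0 | 0 | 5% | 2.5% |
| Local effect only | −30 | +15 | −45 | about 100% | about 0% |
| Partial abscopal effect | −30 | −10 | −20 | 65% to about 100% | 38% to 78% |
| Complete abscopal effect | −30 | −30 | 0 | 5% | over 99% |
| Nothing works, unequal growth | +20 | +5 | +15 | 42% to over 99% | below 1% |

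D gives the same answer for a complete abscopal effect as for no effect with equal growth, and its strongest signal when the effect is purely local. N separates these cases. The last row shows that D can also depart from zero with no treatment effect, if the re-irradiated lesion was growing faster than the one left alone.

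**Other endpoints that might fill the gap.** Time to progression of non-irradiated lesions runs from enrolment (sections 7.2.1 and 8.3.2), not from the second course. The 6-week response rate is counted per patient and is not restricted to untreated lesions. Distant control and the general description of efficacy on non-irradiated lesions are not tied to the second course.

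**The case against.** The strongest reply is that the protocol says only that the changes will be compared. It names no subtraction, test or alpha, and the trial is non-comparative. Comparing two changes means measuring both, and a reader shown −30% and −30% would not confuse it with 0% and 0%. The whole-trial endpoints on non-irradiated lesions also mean that out-of-field response is not ignored. This part stands: the data needed are collected, and a reader might wrongly infer that a significance test will be declared abscopal, which the protocol does not say. It does not remove the problem, because the label is still attached to the comparison and no second-course endpoint is defined on untreated lesions.

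Other stronger readings are not supported:

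- *The section 2.2 change cannot be computed because no scan is scheduled at the second SABR.* Table 1 places the second SABR at first progression, which is established by a RECIST scan. The two starting points in 2.2 and 7.2.1 are a wording mismatch.
- *The node rules conflict.* Section 7.2.1 asks for longest diameter according to RECIST 1.1, and Appendix 4 carries the short-axis exception. The wording is loose but largely covered.
- *The contrast is always near zero when nothing works.* That holds only if both lesion types grow alike. Up to three sites may be progressing, so the untreated lesion may or may not be one of them, and the protocol does not settle this.

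**Conclusion.** The measure is wrong as written for this one objective: the irradiated-versus-untreated contrast cannot serve as the second-course abscopal measure. The conclusion rests on the identity D = I − N, with comparison read as a difference. The percentages in the table depend on the assumed SD, correlation and size changes, and only illustrate it.

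The reach is limited. It concerns a secondary objective, in an expected 25 to 30 patients in each of two cohorts, with no decision rule attached. The primary one-year PFS test is unaffected. The general irradiated-versus-non-irradiated comparison in section 7.2.1 carries no abscopal label and is acceptable as description.

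A reader might infer that a better measure would prove an abscopal effect. It would not: all these patients continue atezolizumab and there is no control arm.

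**What to change.** 1. In the synopsis and sections 2.2 and 7.2.1, define the second-course abscopal measure on the non-irradiated measurable lesions alone: their percentage size change, and their response, from the progression-1 scan to 6 weeks after the second SABR.
2. Keep the irradiated-versus-non-irradiated comparison as a description of local effect and remove the abscopal label from it.
3. Use the progression-1 scan as the single reference in 2.2 and 7.2.1, and state that nodes are measured by short axis as in Appendix 4.
4. Treat any before/after growth-rate comparison as supportive only. The interval that ends in progression is selected for high growth, so regression to the mean alone could look like a slowing after SABR.
5. State that the untreated lesions' change cannot be separated from a continued or delayed atezolizumab effect.

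The cost is a change of wording. The progression-1 scan and the 6-week CT are already part of the plan, so closed enrolment is no obstacle. The limit in item 5 remains, and precision will be modest: under the assumptions above, a mean shrinkage of 10% in untreated lesions would be shown in 38% to 78% of trials. Because the trial is open-label and all cohorts are closed to inclusion, the change should be dated and recorded as made at that stage.
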